7.3. Handling of Missing Data

7.3.1. Missing Dates

In cases of missing or incomplete dates (e.g., AE and concomitant medications), the missing component(s) will be assumed as the most conservative value possible. For example, AEs with missing start dates, but with stop dates either overlapping into the treatment period or missing, will be counted as treatment-emergent, taking the worst-case approach. When partial dates are present in the data, both a partial start date and/or a partial stop date will be evaluated to determine whether it can be conclusively established that the AE started prior to the start of study drug or ended prior to the start of study drug. If the above cannot be conclusively established based on the partial and/or present dates, then the AE will be considered as treatment-emergent. Actual data values as they appear in the original case report forms (CRFs) will be presented in the data listings.

7.3.2. Missing Assessment

Randomized subjects discontinued from the study due to any cause prior to Day 22 will be considered as not developing *S. aureus* pneumonia by SDO1 for the primary efficacy analysis.

Randomized subjects that are non-informative (i.e. a subject that does not develop SDO1 or SDO2 of *S. aureus* pneumonia, indeterminate, or dies before Day 22) will be censored for the Kaplan-Meier analysis unless it is noted otherwise.

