5.2.2. Sponsor-Defined Outcome of *S. aureus* Pneumonia

Sponsor-Defined Outcome (SDO) of *S. aureus* pneumonia will be determined programmatically based on the data and the manual review conducted at Review Meetings per the POP.

Each randomized subject will be evaluated for the occurrence of *S. aureus* pneumonia between Randomization and up to, but not including, Day 22. In order to assign a SDO, the following assessments will be made based on available data:

1. Microbiological Assessment
2. Chest Imaging Assessment
3. Clinical Assessments
 - a. Respiratory
 - b. Signs and Symptoms
4. Operational Assessments

There will be 2 SDO definitions for data analysis: SDO1 and SDO2. The 2 definitions will need to satisfy the 4 assessments above and differ only on the clinical assessments. SDO1 will meet either respiratory OR signs and symptoms requirements while SDO2 will meet both respiratory AND signs and symptoms requirements.

The individual assessments for each randomized subject will be collapsed to assign an SDO1/SDO2 of Yes, No, Indeterminate (i.e. insufficient data to assign a SDO of Yes or No), or Censored (i.e. subject died prior to the Day 22 assessment) based on the mutually exclusive, hierarchical rules specified in the POP.

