7.11.1. Primary Efficacy Endpoint

The primary efficacy endpoint is whether the subject has or has not developed *S. aureus* pneumonia up to, but not including, Day 22 in the MITT Population. For the primary analysis, whether the subject has or has not developed *S. aureus* pneumonia will be based on sponsor defined outcome (SDO1).

The primary analysis is based on comparing two proportions of subjects who develop *S. aureus* pneumonia by SDO1 up to, but not including, Day 22. For each arm, the empirical proportion is defined by a ratio, which is the number of *S. aureus* pneumonia events divided by the total number of subjects in the arm. The inference about the difference of two population rates is based on the empirical counterpart. Specifically, the point estimate, 95% confidence interval and p-value for the rate difference. If subjects discontinued from the study due to any cause prior to Day 22, it will be considered as not developing *S. aureus* pneumonia by SDO1 for the primary efficacy analysis.

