7.11.2. Additional Analyses for *S. aureus* Pneumonia

Analyses of the primary efficacy endpoint will also be performed based on the ITT and PP Populations.

The following additional analyses will be performed in the MITT and PP Populations:

- The primary efficacy analysis, based on comparing two proportions of subjects who develop *S. aureus* pneumonia by SDO2 up to, but not including, Day 22. If subjects discontinued from the study due to any cause prior to Day 22 it will be considered as not developing *S. aureus* pneumonia for this analysis by SDO2.
- The primary analysis is based on comparing two proportions of subjects who develop *S. aureus* pneumonia by SDO1 up to, but not including, Day 22. For each arm, the empirical proportion is defined by a ratio, which is the number of *S. aureus* pneumonia events divided by the total number of subjects in the arm. The inference about the difference of two population rates is based on the empirical counterpart. Specifically, the point estimate, 95% confidence interval and p-value for the rate difference. If subjects discontinued from the study due to any cause prior to Day 22, it will be considered as developing *S. aureus* pneumonia by SDO1 and SDO2.
- The Kaplan-Meier analysis will be performed for the proportion of subjects who develop *S. aureus* pneumonia by Day 21 as determined by SDO1. The proportion of subjects who develop *S. aureus* pneumonia up to but not including Day 22 will

be obtained from Kaplan-Meier estimates for each treatment group. The inference about the difference of two rates will be made via the Kaplan-Meier estimates and their corresponding variance estimates in the MITT population. The treatment difference of two rates, the corresponding 95% confidence intervals and p-value will be presented. In addition, the number and percentage of subjects who developed *S. aureus* pneumonia or were censored will be summarized. The Kaplan-Meier estimate of event rates evaluated at Day 21 and the corresponding 95% confidence intervals will be presented for each treatment group. Subjects who did not develop *S. aureus* pneumonia, discontinued from the study, or died prior to Day 22 will be considered censored. For the censored subjects, the last assessment date on which the subject did not develop *S. aureus* pneumonia based on the Investigator's assessment will be used as the date of censoring.

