- The Kaplan-Meier analysis will be performed for the proportion of subjects who develop *S. aureus* pneumonia up to but not including Day 22 as determined by SDO1 and the Review Meeting's determination of *S. aureus* as a causative pneumonia pathogen.
- The Kaplan-Meier analysis will be performed for the proportion of subjects who develop *S. aureus* pneumonia up to but not including Day 22 as determined by SDO2 and the Review Meeting's determination of *S. aureus* as a causative pneumonia pathogen
- The Kaplan-Meier analysis will be performed for the proportion of subjects who develop *S. aureus* pneumonia up to but not including Day 22 as determined by the Investigator's judgement and the Review Meeting's determination of *S. aureus* as a causative pneumonia pathogen.
- An additional Kaplan-Meier analysis will be conducted for subjects with *S. aureus* pneumonia and presumed *S. aureus* pneumonia by SDO1 and SDO2. The presumed *S. aureus* pneumonia population includes those subjects with microbiologic results "Not Done" up to and including Day 7 (presumed *S. aureus* pneumonia).
- A third Kaplan-Meier analysis will be conducted for subjects with *S. aureus* pneumonia including those subjects with microbiologic results "Not Done" up to and including Day 10 (presumed *S. aureus* pneumonia) for both SDO1 and SDO2 populations.
- The proportion of subjects who develop *S. aureus* pneumonia up to but not including Day 22 as determined by the Investigator's judgement and the Review Meeting's determination of *S. aureus* as a causative pneumonia pathogen will be obtained from Kaplan-Meier estimates for each treatment group. Discontinuation from the study due to any cause up to but not including Day 22 will be considered as an 'Event'.
- The proportion of subjects who develop *S. aureus* pneumonia up to but not including Day 22 as determined by the Investigator's judgement and the Review Meeting's determination of *S. aureus* as a causative pneumonia pathogen will be

- obtained from Kaplan-Meier estimates for each treatment group incorporating censoring. Discontinuation from the study due to any cause up to but not including Day 22 will be considered censored.

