- The proportion of subjects who develop either *S. aureus* pneumonia up to but not including Day 22 as determined by the Investigator's judgement and the Review Meeting's determination of *S. aureus* as a causative pneumonia or another *S. aureus* infection up to but not including Day 22 will be obtained from Kaplan-Meier estimates for each treatment group. Discontinuation from the study due to any cause up to but not including Day 22 will be considered as an 'Event'.
 - The proportion of subjects who develop either *S. aureus* pneumonia as determined by the Investigator's judgement and the Review Meeting's determination of *S. aureus* as a causative pneumonia or another *S. aureus* infection up to but not including Day 22 will be obtained from Kaplan-Meier estimates for each treatment group incorporating censoring. Discontinuation from the study due to any cause up to but not including Day 22 will be considered censored.
 - The proportion of subjects who develop *S. aureus* pneumonia by Day 90 as determined by the Investigator's judgement will be obtained from Kaplan-Meier estimates for each treatment group. Discontinuation from the study due to any cause prior to Day 90 will be considered as an 'Event'.
 - The proportion of subjects who develop *S. aureus* pneumonia by Day 90 as determined by the Investigator's judgement will be obtained from Kaplan-Meier estimates for each treatment group incorporating censoring. Discontinuation from the study due to any cause prior to Day 90 will be considered censored.
 - In addition, the two-sided statistical test with 5% false positive rate for the treatment difference will be conducted based on the difference of two observed proportions of subjects who develop *S. aureus* pneumonia before Day 22 by both SDO1 and SDO2 populations. The treatment difference of two proportions, the corresponding 95% confidence intervals and p-values will also be provided based on a Wald test on equality of proportions.

The number and percentage of subjects with SDO1 and SDO2 of *S. aureus* pneumonia, no *S. aureus* pneumonia, indeterminate, and censored in each treatment group will be summarized descriptively.

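### The Kaplan-Meier analyses that censor deaths report one minus Kaplan-Meier as the proportion developing S. aureus pneumonia, which overstates that proportion in each arm because death is a competing event

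*SAP*

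**What the plan says.** SAP 7.3.2 calls subjects non-informative if they do not develop the outcome, are indeterminate, or die before Day 22, and says that they "will be censored for the Kaplan-Meier analysis unless it is noted otherwise". SAP 5.2.2 gives such deaths their own outcome category: "Censored (i.e. subject died prior to the Day 22 assessment".

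The SDO1 Kaplan-Meier analysis in SAP 7.11.2 repeats the rule: subjects without pneumonia, or who "discontinued from the study, or died prior to Day 22 will be considered censored". The same bullet says that the proportion developing S. aureus pneumonia before Day 22 comes from the Kaplan-Meier estimates, and that "The inference about the difference of two rates will be made via the Kaplan-Meier estimates and their corresponding variance estimates", with a 95% confidence interval and a p-value.

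Three Kaplan-Meier bullets in 7.11.2 use another rule. Two state "Discontinuation from the study due to any cause up to but not including Day 22 will be considered as an 'Event" and one, for Day 90, states "Discontinuation from the study due to any cause prior to Day 90 will be considered as an 'Event". Each is paired with a version that censors discontinuation.

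The primary analysis (SAP 7.11.1) is not Kaplan-Meier. It is a crude proportion, "the number of *S. aureus* pneumonia events divided by the total number of subjects in the arm", with the rule "If subjects discontinued from the study due to any cause prior to Day 22, it will be considered as not developing" pneumonia.

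Neither document names a competing-risk estimator.

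**The concern.** The SAP states what these analyses are meant to estimate: the share of subjects who develop S. aureus pneumonia by a given day. That is an observable proportion. Censoring a death treats the subject as still able to develop pneumonia later, at the rate seen in survivors. One minus Kaplan-Meier then estimates a hypothetical risk in which nobody dies first, and that risk is at least as high as the observable proportion.

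Deaths should not be rare here. Subjects are mechanically ventilated, the eligibility criteria screen only for expected death within 72 hours, and 28-day all-cause mortality is a secondary endpoint. The Kaplan-Meier figures would therefore differ from the primary crude proportions even with no loss to follow-up, and a reader could take the gap for a finding when it comes only from the estimator.

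**Working it through.** **1. The plan's own figure.** Inputs from SAP section 6: 25% vs 12.5%, two-sided 0.05, 80% power. With the pooled-variance formula and mean rate 0.1875:

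n per arm = [1.960·√(2·0.1875·0.8125) + 0.842·√(0.25·0.75 + 0.125·0.875)]² / 0.125² = 151.9, so 152.

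152/(1 − 0.14) = 176.7, so 177 per arm and 354 in total. The stated sample size reproduces, and the two rates are used below as the true proportions.

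**2. How many analyses are involved.** SAP 7.11.2 has twelve Kaplan-Meier bullets. Three count discontinuation as an event. The other nine repeat the censoring rule or fall under the default in 7.3.2.

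**3. Formula.** Let c be the true proportion with pneumonia by Day 21 and m the proportion who die first without it. With constant hazards, the share free of both is 1 − c − m, and pneumonia makes up c/(c + m) of the total hazard. With deaths censored:

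1 − KM = 1 − (1 − c − m)^(c/(c+m)).

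Example with m = 20% (assumed):
- placebo: 1 − 0.55^(0.25/0.45) = 28.3%
- ASN100: 1 − 0.675^(0.125/0.325) = 14.0%

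**4. Equal mortality (m assumed; differences taken before rounding).**

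| m, both arms | Placebo (true 25%) | ASN100 (true 12.5%) | Difference (true 12.5) | Risk ratio (true 0.50) |
|---|---|---|---|---|
| 10% | 26.5% | 13.2% | 13.3 | 0.499 |
| 20% | 28.3% | 14.0% | 14.2 | 0.496 |
| 30% | 30.4% | 15.0% | 15.4 | 0.493 |

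The excess is 1.5 to 5.4 points on placebo and 0.7 to 2.5 on ASN100.

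**5. Early pneumonia.** A daily calculation with 80% of pneumonias spread over the first 7 days and deaths spread evenly over 21 days gives differences of 12.9, 13.4 and 13.9 points for m = 10%, 20% and 30%.

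**6. Unequal mortality (placebo vs ASN100, constant hazards).**
- 30% vs 15% deaths: 30.4% − 13.6% = 16.8 points
- 10% vs 30% deaths: 26.5% − 15.0% = 11.5 points

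**7. The two estimators answer different questions.** Suppose arm A has 20% pneumonia and 15% deaths: 1 − KM = 21.8%, a cumulative pneumonia hazard of −ln(1 − 0.218) = 0.246.
- Arm B has the same pneumonia hazard and 25% deaths: 1 − KM is again 21.8%, but the actual proportion with pneumonia falls to 18.7%.
- Arm B instead has the same actual proportion (20%) and 25% deaths: 1 − KM is 23.3%, because its pneumonia hazard must be higher.

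**The case against.** The strongest reply is that the observable proportion is already the primary analysis. It divides events by everyone in the arm. If deaths before pneumonia are non-events, it equals the Aalen-Johansen estimate when follow-up is otherwise complete. It is repeated for ITT and PP and for SDO2. The Kaplan-Meier analyses are headed as additional and do not bear on the primary conclusion or the sample size. Outcome categories and 28-day mortality are also tabulated by arm, so an imbalance in deaths would be visible. All of this stands, and it limits the point to the additional analyses.

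Second, one minus Kaplan-Meier is not wrong in itself. Under independent censoring it reflects the pneumonia hazard alone, and step 7 shows that cumulative incidence is the quantity that moves with mortality: it can make the arm with more deaths look protected. This also stands. It argues for reporting both, but it does not make one minus Kaplan-Meier the proportion that the SAP says it is.

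The text invites several stronger readings that the documents do not support:
- **Every Kaplan-Meier analysis censors deaths.** The default has an exception clause, and three bullets count discontinuation from any cause as an event. Whether death is included is unclear, since the SDO1 bullet lists discontinuation and death separately.
- **The arm difference is always inflated.** Step 6 shows that it can fall below 12.5 points.
- **The excess is always larger in the arm with more deaths.** It also depends on the pneumonia rate. With 25% pneumonia and 15% deaths the excess is 2.3 points (27.3% − 25%). With 12.5% pneumonia and 25% deaths it is 2.0 (14.5% − 12.5%).
- **A mortality imbalance creates a spurious pneumonia effect.** Equal pneumonia hazards give equal Kaplan-Meier estimates. The 1.5-point gap in the last case of step 7 (23.3% − 21.8%) reflects unequal hazards, and it is small beside a standard error of √(2·0.2·0.8/152) = 4.6 points.

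**Conclusion.** The point holds for the nine Kaplan-Meier analyses that censor deaths: the quantity they name and the estimator they use do not match, and the stated proportion is overstated in each arm. At assumed equal mortality of 10% to 30% with constant hazards, the difference is reported as 13.3 to 15.4 points instead of 12.5, or 12.9 to 13.9 if pneumonia occurs early. The risk ratio barely changes. With enough excess mortality on ASN100 the difference shrinks.

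These sizes rest on assumed mortality, on the hazard shapes stated, and on deaths being unrelated to pneumonia risk given the arm. If dying patients have a different pneumonia risk, one minus Kaplan-Meier is also biased as a hypothetical risk, in an unknown direction.

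A reader might infer that the primary result is compromised. The documents do not support that, provided deaths count as non-events in the crude proportion. The SAP does not say so outright, so it should.

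**What to change.** In SAP 7.3.2 and 7.11.2:

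- For the nine analyses, estimate the proportion in each arm and the difference with its 95% confidence interval by the Aalen-Johansen cumulative incidence function. Treat death before the event as a competing event, and censor only withdrawal or loss to follow-up.
- Keep Kaplan-Meier beside it, labelled as a cause-specific (hazard-based) analysis, and do not describe its output as the proportion who develop pneumonia.
- Read both with mortality by arm, because cumulative incidence falls when mortality rises.
- State whether death counts as discontinuation in the three event-coded analyses and in the primary rule (7.3.2 and 7.11.1). For the Day 90 analyses, also say how deaths from Day 22 onward are handled, since 7.3.2 speaks only of deaths before Day 22.

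The cost is SAP wording, some programming with a standard method, and a second estimand to explain in the report. No new data are needed, and SAP section 3 allows changes before unblinding.

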7.3.3. Other Missing Data

Other missing values will not be imputed and only observed values will be used for reporting of descriptive statistics unless otherwise stated.

7.4. Baseline Definition

For all efficacy and safety endpoints, baseline is defined as the last measurement or assessment prior to the first and only dose of study drug.

7.5. Relative Day

The date of the initiation of study drug administration will be considered relative day 1, relative days will be calculated as follows only when the full assessment date is known (i.e., partial dates will have missing relative days):

For days before the initiation of study drug administration:

Relative Day = Date of Assessment – Date of the initiation of study drug administration

For days on or after the initiation of study drug administration:

Relative Day = Date of Assessment – Date of the initiation of study drug administration + 1

7.6. Interim Analysis

One interim analysis will be conducted during the study, when approximately 125 subjects have reached Day 22. The interim analysis is for futility assessment of the study, and for a potential study sample size adjustment. The futility assessment is based on an unblinded efficacy evaluation while any sample size adjustment result from a review of blinded data pooled across the treatment arms. The interim analysis of futility assessment will be reviewed by an independent Data Review Committee. The details of the interim analysis are described in the Data Monitoring Committee Charter dated 25-June-2018.

7.7. Subject Disposition

Subject disposition will be summarized for the ITT Population for each treatment group and in total. The following subject disposition categories will be included in the summary for the ITT Population:

- Subjects who randomized,
- Subjects who received any study drug,
- Subjects who completed the study assessments through Day 22,
- Subjects who did not complete the study assessments through Day 22,

- Subjects who completed the study assessments by Day 28,
- Subjects who did not complete the study assessments by Day 28,
- Subjects who completed the study assessments through Day 90,
- Subjects who did not complete the study assessments through Day 90, and
- Subjects who completed assessments through Day 22, but did not complete the study assessments through Day 90.

For subjects who did not complete the study assessments through Day 90, a summary will be provided by reason of discontinuation. In addition, the total number of subjects for each defined population will be tabulated.

7.8. Demographic and Baseline Characteristics

Demographic information including sex, race, ethnicity, corrected randomization stratification factor (receipt or non-receipt of concomitant anti-staphylococcal antibiotics at the time of randomization that are potentially active against *S. aureus* pneumonia), age (as a continuous variable and categorized as <55, 55 - <65, 65 - <75 and 75 years), height, weight, and BMI will be summarized by treatment group for the ITT, MITT, PP, PK, and Safety Populations.

7.9. Medical History

Medical history will be collected at the screening visit and randomization visit if changes occurred since the Screening Visit. Only adverse events that were considered to be study procedure related were to be reported between the first study screening visit and randomization. Therefore, any changes in the subject's medical condition during this period were captured as medical history.

All reported medical history conditions will be listed by subject.

7.10. Prior and Concomitant Medications/Procedures

Prior and concomitant medications will be coded using the World Health Organization (WHO) Drug Dictionary (Sept 2016E B2). Concomitant procedures will be coded using the Medical Dictionary for Regulatory Activities (MedDRA, Version 19.1).

Prior medications are medications used before the initiation of study drug administration. Any medications used on or after the initiation of study drug administration will be included as concomitant medications. Hence medications ongoing at start of study medication will be counted as both prior and concomitant medication.

The number and percentage of subjects taking prior medications will be summarized for the ITT Population by anatomic therapeutic chemical (ATC) class and preferred term for each treatment group and overall.

The number and percentage of subjects taking concomitant medications will be summarized for the ITT Population by anatomic therapeutic chemical (ATC) class and preferred term for each treatment group and overall.

The number and percentage of subjects receiving concomitant procedures will also be summarized for the ITT Population by system organ class (SOC) and preferred term for each treatment group and overall.

Prior and concomitant medications/procedures will be listed by subject.

